10.2 Secondary study parameter(s)

The data will be analyzed with Linear Mixed Models (LMMs). LMMs model data from repeated measurements (where measurements from the same individual cannot be assumed to be independent) by including a separate model intercept for each longitudinal study unit (i.e. individual). Treatment group and timepoint will be included as fixed effects, while the study participant will be included as a random effect. Additionally, covariates will also be included as fixed effects: study location, age, gender, baseline value of the outcome parameter. An interaction term

between the effect of time and the effect of treatment groups will also be included in order to assess whether the outcome in question is differentially affected by the Lacprodan® OPN-10 intervention compared to placebo.

Model goodness-of-fit will be assessed and model assumptions (linearity, homoscedasticity, linearity of residuals, non-collinearity of parameters) will be checked.

In cases where the outcome distribution shows departure from normality, the outcome parameter of the LMM will be log-transformed.

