2 OBJECTIVES

2.1 Primary Objective:

To assess the percentage of responders to hepatitis B vaccination (i.e. attaining anti-hepatitis B antibody titres beyond 10 IU/L) in healthy elderly receiving a daily dose of Lacprodan® OPN-10, compared to a placebo product.

2.2 Secondary Objectives:

- Compare the change in serum anti-hepatitis B antibody titres from baseline (V1) to 14 days after the second vaccination (V6) between treatment groups
- Compare the change in serum anti-hepatitis B antibody titres from baseline (V1) to 14 days after the third vaccination (V7) between treatment groups
- Compare the change in circulating cytokines from baseline to 8 weeks intervention (V4) and at the end of the study (V7) between treatment groups
- Quantify plasma levels of hOPN and bOPN at baseline, and at 4 weeks and 8 weeks intervention
- Determine whether intake of OPN-10 affects plasma levels of hOPN.
- Compare the change in serum LPS binding protein (LBP) from baseline to 8 weeks intervention between treatment groups
- Compare the incidence of self-reported URTI or LRTI during the trial, between treatment groups using weekly reports of symptoms related to upper and lower respiratory tract infections Assess the safety of the selected intervention dose, including effects on markers of bone remodelling

2.3 Exploratory Objectives:

[figure not shown]
- Compare the change from baseline in plasma brain-derived neurotrophic factor (BDNF) after 8 weeks intervention between treatment groups (optional)
- Compare the change in faecal microbiota composition after 8 and 14 weeks intervention between treatment groups (optional)

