4.2 Inclusion criteria

In order to be eligible to participate in this study, a subject must meet all of the following criteria:

Substantial

- 1. Age ≥60 and healthy
- 2. Self-reported regular Dutch eating habits as assessed by questionnaire (3 main meals per day)
- 3. Anti hepatitis B antibody titer ≤ 4 IU/L
- 4. Non-smokers (ex-smokers can participate)
- 5. BMI ≥22 and ≤30
- 6. In good health as assessed during screening, and the medical investigator's professional judgment
- 7. Adherence to habitual diet, no changes during study period
- 8. Signed informed consent

Procedural:

- 9. Ability to follow Dutch verbal and written instructions
- 10. Willing to accept disclosure of the financial benefit of participation in the study to the authorities concerned
- 11. Willing to accept use of all encoded data, including publication, and the confidential use and storage of all data for at least 15 years
- 12. Willing to comply with study procedures, including intake of study products and collection of stool and blood samples
- 13. Willingness to give up blood donation starting at screening and during the entire study

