4.4 Sample size calculation

Sample size calculation was based on a publication by Albers et al. (Albers et al. 2003). In this study (with another nutritional intervention), seroconversion after hepatitis B vaccination in the placebo group was 33%, and it was 63% in the active group. For the present study, we assumed seroconversion of 25% in the placebo group. To be able to detect a doubling of seroconversion (to 50%) in the active group, a sample size of 58 subjects per group was calculated (Sample Size Calculator (clincalc.com)), with an alpha of 0.05 and a power of 0.8. Taking into account a drop-out rate of ~15%, we propose to include 70 subjects per group.

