10 STATISTICAL ANALYSIS

A detailed Statistical Analysis Plan (SAP) will be prepared and signed-off by an independent statistician, ultimately before database lock.

Descriptive information: all parameters studied will be described as mean and standard deviation when normal distribution has been ascertained. When the data are not normally distributed, descriptive values will be represented by median and interquartile range. In all cases the number of observations per parameter will be provided.

Throughout the study a p-value of lower than 0.05 will be considered to detect a statistically relevant difference, applying two-sided testing.

In the SAP, the intention-to-treat (ITT) population and the per protocol (PP) population will be defined. In a blind data review meeting the criteria for excluding specific subjects from the PP population will be applied.

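### A random-intercept model with one residual variance would miscalibrate the per-visit titre comparisons at V6 and V7 if titre spread differs between those visits

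*Protocol*

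**What the plan says.** Protocol section 10.2 specifies linear mixed models for the secondary parameters. The within-subject part is described twice: the model works "by including a separate model intercept for each longitudinal study unit (i.e. individual", and treatment and timepoint are fixed effects "while the study participant will be included as a random effect". A treatment-by-time interaction is included. Study location, age, gender and the baseline value of the outcome are fixed covariates. The section plans a check of homoscedasticity, and a log transform of the outcome where its distribution departs from normality. It names no visit-specific variance and no remedy if variances prove unequal.

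The titre objectives in section 2.2 are two separate comparisons: change from V1 to V6, two weeks after the second vaccination, and change "from baseline (V1) to 14 days after the third vaccination (V7) between treatment groups". Section 8.1.2 lists the same two endpoints. Eligibility (section 4.2) requires "Anti hepatitis B antibody titer ≤ 4 IU/L" at V1. Tests are at the 5% level, "applying two-sided testing" (section 10). Section 10 leaves the details to an SAP that is not shown here.

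**The concern.** A random intercept with a single residual variance implies the same variance at every visit. Hepatitis B titre is an unlikely candidate for that. Subjects start near the floor, and the sample becomes a mixture of people still near it and people who have responded. The proportions of that mixture change between the second and third vaccination, so the spread probably changes too.

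If it does, the model pools the two variances and uses the pooled value for the treatment contrast at both visits. One visit gets a standard error that is too small, and so too many false positives. The other gets one that is too large, and so loses power. These are the first two secondary endpoints listed and the continuous counterpart of the primary endpoint, so a miscalibrated p-value at V7 could colour how the primary result is read.

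**Working it through.** **The plan's own figure.** The protocol gives no SD, standard error or power for titre. Its only sample size figure is for the primary endpoint (section 4.4): "we assumed seroconversion of 25% in the placebo group", 50% in the active group, "with an alpha of 0.05 and a power of 0.8". With pooled proportion 0.375:

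n = [1.96·√(2·0.375·0.625) + 0.8416·√(0.25·0.75 + 0.5·0.5)]² / 0.25² = (1.342 + 0.557)² / 0.0625 ≈ 57.7, so 58 per group.

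This agrees with the protocol. It does not bear on the titre model, because group size cancels from the ratios below.

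**Setup.** Take V1 as covariate only, with V6 and V7 as the outcome rows. Let the residual log-titre SD be 1 at V6 and r at V7 (assumed). With complete data, the random-intercept model's variance for a visit mean uses the average A = (1 + r²)/2 at both visits. Hence:

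- ratio of model SE to true SE: √A at V6 and √(A/r²) at V7;
- actual type I error: 2·[1 − Φ(1.96 × ratio)].

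| r (assumed) | A | SE ratio V6 | Type I V6 | SE ratio V7 | Type I V7 |
|---|---|---|---|---|---|
| 0.8 | 0.820 | 0.906 | 7.6% | 1.132 | 2.7% |
| 1.0 | 1.000 | 1.000 | 5.0% | 1.000 | 5.0% |
| 1.25 | 1.281 | 1.132 | 2.7% | 0.906 | 7.6% |
| 1.5 | 1.625 | 1.275 | 1.2% | 0.850 | 9.6% |
| 2.0 | 2.500 | 1.581 | 0.2% | 0.791 | 12.1% |

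**Power at V6.** For an effect that a correctly calibrated test would detect with 80% power, the power is Φ(1.96 + 0.8416 − 1.96·√A). This gives 72%, 62% and 38% for r = 1.25, 1.5 and 2.0.

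**Simulation.** With 20,000 trials per ratio, 60 per arm and V6–V7 correlation 0.7, rejection for r = 1.25, 1.5 and 2.0 was 8.0%, 9.6% and 12.4% at V7, and 2.8%, 1.3% and 0.2% at V6. Visit-specific variances gave 4.7–5.1%. A mixed-model fit on log10 titre with assumed SDs 0.2, 0.5 and 0.8 at V1, V6 and V7 (r = 1.6, 58 per group, 400 runs) gave 10.0% at V7 and 0.8% at V6.

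**Is r different from 1?** The documents do not say. As an illustration, suppose 10–15% have responded by V6 (assumed) and 25–50% by V7 (the section 4.4 planning rates). The between-component part of the variance is proportional to p(1 − p). The SD ratio from that part alone runs from √(0.1875/0.1275) = 1.21 to √(0.25/0.09) = 1.67. Within-component spread would alter this. Because p(1 − p) falls once p passes one half, a higher response could push the ratio the other way; section 7.4 mentions about 75% seroprotection under the accelerated schedule.

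**The interaction contrast.** For V7 minus V6, the model variance is 2(A − c), where c is the V6–V7 covariance. That equals 1 + r² − 2c, the true variance, so its SE ratio is 1.00 whatever r is.

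**If V1 were also an outcome row.** With assumed SDs 0.2, 0.8 and 0.8 (V1 correlation with later visits 0.2, V6–V7 correlation 0.5–0.8), the change-from-V1 tests reject 4.9–7.9% even though V6 and V7 have equal spread. With V1 as covariate only, the same SDs give 5.0%.

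**The case against.** The strongest reply is that residual covariance is ordinary SAP content, that section 10.2 never writes of a common residual variance, and that a random participant effect can coexist with visit-specific residual variances. It is right that the single variance is the default reading and not written text. But section 10.2 does state a within-subject structure, and an SAP that follows it literally arrives at this model.

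Second, section 10.2 plans a homoscedasticity check and a log transform. Both are real. However, the check has no stated consequence, and the transform is triggered by non-normality. It need not equalise the spread at V6 and V7: all the ratios above are already on the log scale.

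Third, the interaction is the term that section 10.2 says will show a differential effect, and with baseline as covariate only its V7-minus-V6 contrast is correctly calibrated. That stands. It does not answer the objectives in section 2.2, though, which ask for the group difference at each visit.

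Two stronger readings are tempting and are not supported. A reader might infer that the 4 IU/L cap at V1 is itself what breaks the model. With baseline as a covariate, V1 does not enter the residuals and the cap does no harm. It would add to the problem only if V1 were also kept as an outcome row, which section 10.2 does not say. A reader might also infer that the V7 test is certain to be anti-conservative. Without titre SDs, neither the direction nor the size is fixed by the protocol.

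**Conclusion.** The point holds conditionally. If the model in section 10.2 is fitted with its default single residual variance, if the treatment contrasts are taken at each visit, and if log-titre spread differs between V6 and V7, the standard errors are wrong in opposite directions at the two visits. For assumed V7:V6 SD ratios of 1.25 to 2.0, false positives at V7 are about 7.6–12.1% against a nominal 5%, and the V6 test becomes conservative (2.7% down to 0.2%). The V7-minus-V6 interaction contrast, the primary Fisher's exact test and the sample size of 58 per group before drop-out are untouched. This is a weakness in a secondary analysis that is nearly free to remove, and it does not threaten the primary conclusion.

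**What to change.** In section 10.2, for titre and the other outcomes with two or more post-baseline visits (cytokines, OPN), replace the random intercept by a repeated-measures model with unstructured covariance across the post-baseline visits. State that baseline enters as a covariate only and not as an outcome row, and that the treatment contrast is estimated at each visit. A baseline-adjusted ANCOVA at each visit is an acceptable alternative and gives nearly the same answer when few data are missing. Carry the same wording into the SAP before unblinding.

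The cost is a sentence or two of text, a different covariance option in the software, and one or two more covariance parameters, which a trial of this size can estimate without difficulty.

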3 STUDY DESIGN

The study is designed as a double-blind, randomized, placebo-controlled trial, with two treatment arms.

After an 8-week intervention period, all subjects will receive a hepatitis B vaccination, administered by intramuscular injection, at weeks 8, 10 and 12. Vaccination response will be measured at weeks 12 and 14. The intervention will be continued until the end of the study at week 14.

NL81499.028.22 BOFEI

The study will be conducted at the clinical research facilities of NIZO in Ede and EBMR in Almere.. For the clinical conduct within these facilities, EB Medical Research (Almere) will be responsible. The responsibilities of EB Medical Research include the recruitment and screening of study subjects, conduct of the study visits and medical supervision.

The schedule of assessments at the different visits is as follows:

	V1	V2	V3	V4	V5	V6	V7
	Screening	Week 0	Week 4	Week 8	Week 10	Week 12	Week 14
		Day 0	Day 28	Day 56	Day 70	Day 84	Day 98
Screening	х						
Eligibility check	х						
Clinical conduct							
Randomization		Х					
Study product supply		Х		х	х	х	
HepB Vaccination				Х	Х	Х	
Blood sample collection		Х	X	X		X	Х
Serum anti HB titer	Х					X	X
Serum chemistry & hematology	Х	Х	X	X			
Plasma circulating cytokines		X		X			Х
Plasma/serum P1NP		Х		X			
Plasma/serum CTX-1		Х		X			
Plasma levels of OPN		X	X	X			
Serum LPS binding protein (LBP)		X		X			
Faecal sample collection		Х		Х			х
OPTIONAL BDNF		Х	-	Х		-	
AE registration		Х	Х	Х	х	Х	Х

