8.1.2 Secondary study parameters/endpoints

- Change in serum anti-hepatitis B antibody titres from baseline (V1) to 14 days after the second vaccination (V6) and 14 days after the third vaccination (V7)
- Change in circulating cytokines from baseline to 8 weeks intervention (V4) and to the end of the study (V7). The analyses will be performed at NIZO with a multiplex assay in duplicate. Results will be displayed in pg/ml (dependent on the actual outcomes). In principle, the following set of cytokines will be analysed; however, the final choice of the most relevant cytokines may be slightly different, depending on the outcomes of ongoing analytical validation experiments.
 - Interleukin 6 (IL-6)
 - Interleukin 10 (IL-10)
 - Interferon y (IFNy)
 - Tumour necrosis factor α (TNFα)
 - Chemokine (C-C motif) ligand 3 (CCL-3)
 - Interleukin 15 (IL-15)
 - Interleukin 17a (IL-17a)
 - Interleukin 4 (IL-4)
 - Interleukin 2 (IL-2)
 - Interleukin 2RA (IL-2RA)
- Change in serum levels of P1NP and CTX-1 (as markers of bone formation and bone resorption) from baseline to 8 weeks intervention. Analyses will be performed by an external routine lab.
- Change in plasma levels of hOPN and bOPN from baseline to 4 weeks and 8 weeks intervention. hOPN and bOPN will be analysed at NIZO with an ELISA assay in duplicate. Results will be displayed in pg/ml (dependent on the actual outcomes).

NL81499.028.22 BOFEI

• Change in serum LPS binding protein (LBP) from baseline to 8 weeks intervention. Serum LBP will be analysed at NIZO with an ELISA assay in duplicate.

- Incidence of self-reported URTI or LRTI during the trial, including weekly reports of symptoms related to upper and lower respiratory tract infections
- Safety monitoring by routine assays for hematology and serum clinical chemistry. Analyses will be performed by an external routine lab.

Table 4 Blood parameters for safety monitoring:

Clinical chemistry	Method	Unit
Serum alkaline phosphatase	Photometry	U/I
Serum alanine aminotransferase (ALAT)	Photometry	U/I
Serum aspartate aminotransferase (ASAT)	Photometry	U/I
Serum triacylglycerols	Photometry	mg/dl
Serum total cholesterol	Photometry	mg/dl
Serum total bilirubin	Photometry	mg/dl
Serum urea	Photometry	mg/dl
Serum Creatinine	Photometry	mg/dl
Serum hs C-reactive protein	Nephelometry	mg/dl
Serum albumin	Nephelometry	mg/dl
Blood Glucose (Sodium Fluoride tubes, NaF)	Photometry	mg/dl
Hematology		
Red blood cell (RBC) count	Flow cytometry	10^12/L

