8.3.2 Screening visit (visit 1)

All study visits are scheduled to take place at NIZO, [name] in Ede or at EB Medical research, [name] in Almere.

The subjects will have a pre-study screening (V1) within 2-4 weeks before visit 2, the start of the intervention period.

During the screening visit, a blood sample will be drawn, for the determination of anti-hepatitis B antibody titer, and for a routine safety panel (clinical chemistry and hematology, as listed under 8.1.2). Body weight and height will be measured. A subject's eligibility will be assessed based on the

lifestyle and health questionnaire, BMI, antibody titer, clinical chemistry and hematology. The medical investigator will inform the subjects about their eligibility in writing. In case of a surplus of eligible participants, random allocation will determine which of these participants will be able to join the study.

During the screening visit, verbal instructions will be provided about the collection of fecal samples. All screened subjects will receive a fecal collection kit before visit 2. This kit will also contain written instructions about the collection of fecal samples.

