13 STRUCTURED RISK ANALYSIS

13.1 Potential issues of concern

a. Level of knowledge about mechanism of action

Overall, there is no single known specific function of bOPN. bOPN has been closely associated with functions involving the immune response (see section 6.2). Few data are available from adult animal models, while, to the best of our knowledge, no data from adult clinical studies have been reported.

b. Previous exposure of human beings with the test product(s) and/or products with a similar biological mechanism

A clinical study has been performed with the test product, in 2 different dosages, in infants from 1 to 6 months of age (see section 6.3). The product was well tolerated, potential beneficial effects were observed. The available study results have supported a positive evaluation of the EFSA NDA Panel of the safety of bOPN as a Novel Food (EFSA NDA Panel 2022).

c. Can the primary or secondary mechanism be induced in animals and/or in *ex-vivo* human cell material?

The whole organism is needed to induce the expected effects, and this study is designed to investigate efficacy in relation to vaccination response, in addition to investigating mechanistic aspects. It is not known yet which are the primary or secondary mechanisms, although it is hypothesized that modulation of the inflammatory response plays an important role.

d. Selectivity of the mechanism to target tissue in animals and/or human beings
Effects on immune cells and inflammatory markers have previously been observed in animal models and/or healthy infants.

e. Analysis of potential effect

The dose of Lacprodan® OPN-10 is based on the doses that have been used in the infant clinical trial, and are far below the NOAEL that has been determined based on toxicological studies.

Because this is the first study with Lacprodan® OPN-10 in adults, potential adverse effects will be monitored and changes in standard clinical chemistry and hematology will be assessed, with particular attention for inflammatory markers.

As human OPN (with a different amino acid sequence compared to bovine OPN) has been found to be associated with some negative health effects, including increased bone resorption, levels of human OPN and markers of bone formation and bone resorption will also be monitored during the study.

f. Pharmacokinetic considerations Not applicable

g. Study population

The study population consists of healthy elderly ≥65 years.

h. Interaction with other products Not applicable

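### Chemistry and haematology are measured twice before treatment, but the model in 10.2 names one baseline value; entering the second as a covariate would gain a little precision at almost no cost

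*Protocol*

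**What the plan says.** The schedule in section 3 marks "Serum chemistry & hematology" at V1, V2, V3 and V4, and Table 5 draws the chemistry, glucose and haematology tubes at both V1 and V2. Section 8.3.2 says that blood is taken at V1 "for a routine safety panel (clinical chemistry and hematology, as listed under 8.1.2", so it is the same panel. V1 falls "within 2-4 weeks before visit 2, the start of the intervention period". Section 8.3.3 draws the V2 sample at the visit where product is first handed out. Table 4 lists "Serum hs C-reactive protein".

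Section 8.1.2 counts "Safety monitoring by routine assays for hematology and serum clinical chemistry" among the secondary parameters, so the linear mixed model of section 10.2 covers it. The covariates there are "study location, age, gender, baseline value of the outcome parameter", with a random intercept per subject and a treatment-by-time interaction.

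Section 10.2 does not name the visit that supplies the "baseline value of the outcome parameter" for these assays. Section 8.3.3 calls V2 the baseline visit, and 13.1(j) gives the safety time points as baseline, week 4 and week 8. Sections 2.2 and 8.1.2 take V1 as baseline for the antibody titre.

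**The concern.** Each subject supplies two pre-treatment readings of every Table 4 parameter. On the natural reading of 10.2, the model uses V2, and V1 serves only to decide eligibility. A marker that varies within a person is measured with error at any one visit, and a second pre-treatment reading can improve the adjustment.

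The stake is the width of the confidence intervals for these parameters. This is the first study of the product in adults, and 13.1(e) promises to look at chemistry and haematology "with particular attention for inflammatory markers". No power is stated for these comparisons, so precision obtained without extra sampling is worth having.

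**Working it through.** **The plan's own figure.** The only sample size in the protocol (4.4) is for the primary endpoint: 25% against 50%, two-sided alpha 0.05, power 0.8. The usual two-proportion formula gives 58 per group, as stated. Inflating for 15% drop-out gives 58/0.85 = 68.2, so 69 against the 70 proposed. The present point does not touch this figure. There is no SD, correlation or power for the Table 4 assays to reproduce.

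**Equal correlation.** A random intercept implies the same correlation r between any two visits. The value of r is an assumption. In units of SD squared, the residual variance at one follow-up visit is:

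- with V2 only: 1 − r²
- with V1 and V2: 1 − 2r²/(1 + r). Here the mean of the two and two separate covariates give the same result.

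| r | V2 only | V1 and V2 | Variance cut | Interval narrower by |
|---|---|---|---|---|
| 0.3 | 0.910 | 0.862 | 5.3% | 2.7% |
| 0.5 | 0.750 | 0.667 | 11.1% | 5.7% |
| 0.7 | 0.510 | 0.424 | 17.0% | 8.9% |
| 0.9 | 0.190 | 0.147 | 22.4% | 11.9% |

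At 58 per group and 80% power, the detectable difference is (1.960 + 0.842) × √(2v/58), where v is the residual variance. It falls from 0.451 to 0.425 SD at r = 0.5, and from 0.372 to 0.339 SD at r = 0.7.

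For the group difference averaged over V3 and V4, the variance is (1 + r)/2 − r² against (1 + r)/2 − 2r²/(1 + r). That is 0.500 to 0.417 at r = 0.5 (16.7% less) and 0.360 to 0.274 at r = 0.7 (24.0% less).

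**Fading correlation.** V1 lies 2 to 4 weeks before V2 and so 10 to 12 weeks before V4. It may predict V4 less well than V2 does. Let a, b and c be the correlations V1–V2, V2–V4 and V1–V4, again assumed.

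- V2 only: 1 − b²
- V1 added as a separate covariate: 1 − b² − (c − ab)²/(1 − a²)
- simple mean: 1 − [(b + c)/2]²/[(1 + a)/2]

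| a, b, c | V2 only | V1 added | Cut | Simple mean | Change against V2 only |
|---|---|---|---|---|---|
| 0.6, 0.5, 0.45 | 0.750 | 0.715 | 4.7% | 0.718 | 4.3% lower |
| 0.7, 0.6, 0.5 | 0.640 | 0.627 | 2.0% | 0.644 | 0.6% higher |
| 0.8, 0.7, 0.6 | 0.510 | 0.506 | 0.9% | 0.531 | 4.0% higher |
| 0.7, 0.6, 0.4 | 0.640 | 0.639 | 0.1% | 0.706 | 10.3% higher |
| 0.8, 0.7, 0.5 | 0.510 | 0.500 | 2.0% | 0.600 | 17.6% higher |

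The gain from adding V1 vanishes when c = ab, that is, when V1 tells nothing about V4 beyond what V2 tells. The simple mean forces equal weights and can lose precision. Separate covariates let the data set the weights. With 2 × 58 = 116 subjects, one more coefficient costs roughly 1/116, or 0.9%, of the variance, so at the bottom of this range the net gain is nil.

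**The case against.** The strongest objection is that this belongs in the SAP, which is not at hand. Section 10 defers detail to it, 10.2 does not say which visit is the baseline for these assays, and nothing excludes V1 from the model. A reader might infer that the protocol discards V1; no sentence says so, and an SAP could use both readings without contradicting the protocol. That stands. What remains is that 10.2 already sets out a covariate list, and read as written that list has one baseline term.

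Second, the gain rests on correlations that the protocol does not give, and it can be close to nothing. That also stands, and is why both structures are shown.

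Third, the two readings may not be interchangeable. Eligibility is judged partly on V1 results, so V1 values may be range-restricted. Section 8.3.2 does not itself state fasting at V1, although 5.2 asks for it on visit days; this matters for glucose and triacylglycerols. These points weaken the case for averaging more than the case for a separate covariate, which remains a valid pre-treatment variable.

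Fourth, 13.1(j) describes review of individual results, which no covariate choice affects. A reader might infer that a safety signal would be missed without V1. The documents do not support that: the effect is on the width of intervals for group comparisons only.

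**Conclusion.** This is a small missed efficiency in a valid analysis, not an error or a contradiction. Adjusting for one baseline value introduces no bias. Adding V1 would cut residual variance at a visit by about 5% to 22% if all visits correlate equally at 0.3 to 0.9, the structure the random intercept implies, and by about 0% to 5% in the fading-correlation cases tried. All correlations are assumed.

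The gain applies to group differences at a visit or averaged over visits. A contrast of the treatment effect between V3 and V4 gains nothing from a covariate that is constant within a subject. Nor does the point carry over to inflammatory markers in general: the cytokines, like OPN, LBP, P1NP and CTX-1, have V2 as their only pre-treatment sample, and the antibody titre has only V1. The primary Fisher test is unaffected.

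**What to change.** In the SAP or in 10.2, before unblinding and for Table 4 parameters only, state that V2 is the baseline value and that the V1 value enters the model as a second, separate covariate. Put both on the log scale for skewed markers such as hs-CRP. Do not replace them by their simple mean. Keep the single baseline for all other parameters.

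The cost is a sentence or two, one degree of freedom per model, and a rule for a missing V1 or V2 reading that ignores treatment group. Before V1 is used for glucose and triacylglycerols, check that those samples were fasting. No new samples or visits are needed.
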